1.5 HIGH FREQUENCY LOW DOSE SQ RITUXIMAB IN CLL

Unconjugated anti-CD20 mAb are effective and tolerable therapy for CLL and other B cell malignancies but rarely achieve complete remission as single agents and are not curative. Anti-CD20 mAb primary kills B cells by activating the innate immune system i.e. cell mediated cytotoxicity and complement dependent cytotoxicity (CDC). There is appreciable *in vivo* murine and *in vivo* primary human cell data showing that the primary mechanism of removal of opsonized B cells in the circulation is phagocytosis by fixed macrophages in the liver (Kupffer cells) and spleen. [15-23](and unpublished data from [name] lab) The mechanism of cellular cytotoxicity in malignant lymphoid tissue is less well understood but could involve activation of tumor associated macrophages that converts them from supportive to cytotoxic cells. NK cell mediated ADCC has a limited capacity to kill CLL cells *in vitro* and there is no documented cytotoxic role for NK cells in lymphoid tissue. In summary, most anti-CD20 mAb cytotoxicity is mediated by the innate immune system via CDC and macrophage ADCC.

Mechanisms of resistance of B cells to anti-CD20 mAb therapy are not well understood. Circumstantial evidence suggests that treatment efficacy is limited by the finite cytotoxic capacity of the innate immune system. Studies of complement levels after treatment in patients with circulating B cells suggests that depletion of complement is not a major limitation of CDC but are not conclusive. [24, 25] Intrinsic resistance to activated complement system generated membrane attack complexes activated by anti-CD20 mAb has been demonstrated *in vitro*. [26, 27] There is limited data on the cytotoxic capacity of fixed macrophages in humans and no published data on target B cell resistance to ADCC. An important and well documented mechanism of acquired resistance to anti-CD20 mAb therapy is loss of CD20 expression by target cells by trogocytosis as recently reviewed. [28] In brief, administration of large doses of aCD20 mAb rapidly activates the innate immune cytotoxic mechanism followed by rapid loss of cell membrane CD20 (~99%) by the surviving cells. [24] Loss of CD20 occurs by trogocytosis, a mechanism of non-lethal removal of membrane bound immune complexes (e.g. CD20-anti-CD20 mAb) from target cells by effector cells including macrophages, monocytes, and neutrophils. [29] In clinical trials therapy with higher frequency (2-3 x week) lower (20 mg/m²) doses of rituximab did not cause significant loss of CD20. [30, 31] These data support further trials of high frequency low dose rituximab in the management of CLL and other B cell malignancies.

Rituximab is FDA approved for the treatment of CLL based on an overall survival benefit when combined with standard therapy in the first line setting. [3] Subcutaneously administered rituximab is also approved for use in CLL based on non-inferior pharmacokinetics and comparable efficacy. [32-34] Additionally, in a randomized phase 3 trial comparing intravenous vs. subcutaneous rituximab, 77% of patients preferred subcutaneous administration. [35] The most common adverse events (≥20%) observed in patients with FL include infections, neutropenia, nausea, constipation, cough, and fatigue. The most common adverse events (≥20%) observed in patients with DLBCL include infections, neutropenia, alopecia, nausea, and anemia. The most common adverse events (≥20%) observed in patients with CLL were infections, neutropenia, nausea, thrombocytopenia, pyrexia, vomiting, and injection site erythema.

1.6 HYPOTHESIS

Combined BTK inhibitor and anti-CD20 mAb therapy has been shown to be safe and effective for treatment of CLL. [36] The rationale for use of this combination is the disparate mechanisms of actions and assumed differences in tumor cell resistance to cytotoxicity of these drugs. In addition, initiation of therapy with BTK inhibitors frequently causes lymphocytosis by mobilizing CLL cells from lymphoid tissue into the circulation where they are more susceptible to mAb mediated cytotoxicity. We propose that the combination of a BTK inhibitor and kinetically optimized high frequency low dose rituximab therapy will increase the efficacy of therapy for CLL by decreasing the time of achievement of complete response and allowing for shorter and less toxic therapy.

2 OBJECTIVES AND ENDPOINTS

2.1 PRIMARY OBJECTIVE

- To define the clinical efficacy as defined by complete remission rate of acalabrutinib and high frequency low dose subcutaneous rituximab in patients with previously untreated CLL/SLL

2.2 SECONDARY OBJECTIVES

- To describe the rate of MRD negativity using 6-color flow cytometry.
- To define the progression free survival and duration of response in patients treated with the combination.
- To determine the safety of acalabrutinib and high frequency low dose subcutaneous rituximab in this population.

2.3 EXPLORATORY OBJECTIVES

- To determine the effect of high frequency low dose SQ rituximab on circulating CLL cell CD20 expression before and after the addition of acalabrutinib.
- To determine the effects of in vivo exposure of circulating target and effector cells to acalabrutinib on subsequent in vitro anti-CD20 monoclonal antibody induced ADCP, ADCC and CDC.
- To determine the effect of treatment with acalabrutinib and HFLD SQ rituximab on T, B, NK and monocyte immunophenotypes in CLL/SLL patients

Response and efficacy endpoints will be defined as per the guidelines for the diagnosis, response assessment and supportive management of chronic lymphocytic leukemia. [37]

3 ELIGIBILITY CRITERIA

Patients must meet all of the following inclusion criteria and none of the exclusion criteria to be eligible for participation in this study.

3.1 INCLUSION CRITERIA

Patients must meet all of the following inclusion criteria to be eligible for participation in this study:

1. Diagnosis of B-cell CLL or SLL, with diagnosis established according to IWCLL criteria and documented within medical records. Patients must not have received previous therapy for CLL/SLL
2. CLL/SLL that warrants treatment consistent with accepted IWCLL criteria for initiation of therapy. Any one of the following conditions constitutes CLL/SLL that warrants treatment:
 - a. Evidence of progressive marrow failure as manifested by the onset or worsening of anemia and/or thrombocytopenia, or
 - b. Massive (i.e., lower edge of spleen \geq 6 cm below the left costal margin), progressive, or symptomatic splenomegaly, or
 - c. Massive (i.e., \geq 10 cm in the longest diameter), progressive, or symptomatic lymphadenopathy, or
 - d. Progressive lymphocytosis in the absence of infection, with an increase in blood absolute lymphocyte count (ALC) \geq 50% over a 2-month period or lymphocyte doubling time of <6 months (as long as initial ALC was \geq 30,000/L), or
 - e. Autoimmune anemia and/or thrombocytopenia that is poorly responsive to corticosteroids or other standard therapy, or
 - f. Constitutional symptoms, defined as any one or more of the following disease-related symptoms or signs occurring in the absence of evidence of infection:
 - i. Unintentional weight loss of \geq 10% within the previous 6 months, or
 - ii. Significant fatigue (\geq Grade 2), or
 - iii. Fevers $>100.5^{\circ}\text{F}$ or 38.0°C for \geq 2 weeks, or
 - iv. Drenching night sweats for >1 month.
3. Adequate organ system function, defined as follows:
 - a. Absolute neutrophil count (ANC) \geq $0.5 \times 10^9/\text{L}$ and platelet count \geq $30 \times 10^9/\text{L}$
 - b. Total bilirubin \leq 2.5 times the upper limit of normal (ULN) unless due to Gilbert's disease
 - c. Alanine aminotransferase (ALT) and aspartate aminotransferase (AST) \leq 2.5 x ULN if no liver involvement or \leq 5 x the ULN if known liver involvement
 - d. Calculated creatinine clearance >30 mL/min (as calculated by the Cockcroft-Gault formula)
 - e. Patients with PT/INR or aPTT \leq 2xULN.
4. ECOG performance status \leq 2 unless related to CLL.
5. Male or female \geq 18 years of age.
6. Ability to swallow and retain oral medication.

7. Woman of childbearing potential (WOCBP) who are sexually active must use highly effective methods of contraception during treatment and for 2 days after the last dose of acalabrutinib and for 12 months following last dose of rituximab. (see Appendix 3 for examples)
8. Willingness and ability to comply with study and follow-up procedures, and give written informed consent.

3.2 EXCLUSION CRITERIA

Patients who meet any of the following exclusion criteria are not to be enrolled to this study:

1. Patients receiving cancer therapy (i.e., chemotherapy, radiation therapy, immunotherapy, biologic therapy, hormonal therapy, surgery).
 - a. Systemic corticosteroid therapy started prior to study entry is allowed as clinically warranted. Topical or inhaled corticosteroids are permitted.
2. Serologic status reflecting active hepatitis B or C infection. Patients who are hepatitis B core antibody (anti-HBc) positive and who are surface antigen negative will need to have a negative polymerase chain reaction (PCR). Those who are hepatitis B surface antigen (HbsAg) positive or hepatitis B PCR positive will be excluded. Subjects who are hepatitis C antibody positive will need to have a negative PCR result. Those who are hepatitis C PCR positive will be excluded.
3. Known history of HIV.
4. Known histological transformation from CLL to an aggressive lymphoma.
5. Evidence of ongoing systemic bacterial, fungal or viral infection, except localized fungal infections of skin or nails. NOTE: Patients may be receiving prophylactic antiviral or antibacterial therapies at investigator discretion.
6. Live virus vaccines within 4 weeks prior to C1D1 or during rituximab therapy.
7. History of anaphylaxis (excluding infusion related reactions) in association with previous anti-CD20 administration or acalabrutinib.
8. Any severe and/or uncontrolled medical conditions or other conditions that could affect their participation in the study such as:
 - a. Symptomatic, or history of documented congestive heart failure (NY Heart Association functional classification III-IV)
 - b. Uncontrolled cardiac arrhythmia (Patients with controlled atrial fibrillation/flutter are eligible)
 - c. Myocardial infarction within 3 months of enrollment
 - d. Angina not well-controlled by medication
 - e. Poorly controlled or clinically significant atherosclerotic vascular disease including cerebrovascular accident (CVA), transient ischemic attack (TIA), angioplasty, cardiac/vascular stenting within 3 months of enrollment.
 - f. Active bleeding or history of bleeding diathesis (eg, hemophilia or von Willebrand disease).
 - g. Any history of intracranial bleed or stroke within 6 months of first dose of study drug
 - h. Patients with suspected or confirmed PML
 - i. Patients with malabsorption syndrome or gastrointestinal disease that limits absorption of oral medication
9. Malignancy within 2 years of study enrollment except for adequately treated basal, squamous cell carcinoma or non-melanomatous skin cancer, carcinoma in situ of the cervix, superficial bladder cancer not treated with intravesical chemotherapy or BCG within 6 months, localized prostate cancer and PSA <1.0 mg/dL on 2 consecutive measurements at least 3 months apart with the most recent one being within 4 weeks of study entry.

10. Patients with active uncontrolled autoimmune hemolytic anemia or ITP.
11. Inability to discontinue use of strong CYP3A inhibitors. Patients taking moderate CYP3A inhibitors or strong CYP3A inducers are eligible.
12. Requires or receiving anticoagulation with warfarin or equivalent vitamin K antagonists (eg, phenprocoumon) within 7 days of first dose of study drug.
13. Requires treatment with proton pump inhibitors (eg, omeprazole, esomeprazole, lansoprazole, dexlansoprazole, rabeprazole, or pantoprazole) at study entry. Subjects receiving proton pump inhibitors who switch to H2-receptor antagonists or antacids are eligible for enrollment to this study.

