9 STATISTICAL CONSIDERATIONS

9.1 DESIGN

This is a single-arm, single-center prospective study. The complete response rate will be estimated from forty enrolled subjects. An associated 95% two-sided confidence interval will be calculated using exact binomial methods. We anticipate a CR rate of 20%, which would result in a 95% two-sided confidence interval with a width of 26.6% (from 9.1% to 35.6%) for a sample size of 40 subjects. The maximum possible width of a 95% confidence interval using 40 subjects would be 32.4%.

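### The localized prostate cancer exception in exclusion 9 prints its PSA limit in mg/dL, apparently a unit error, so as written the numeric cut-off does no screening

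*Combined protocol and SAP*

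**What the plan says.** Section 3.2, exclusion 9, opens with the general bar and its first exception: "Malignancy within 2 years of study enrollment except for adequately treated basal". Further exceptions follow. The last is "localized prostate cancer and PSA <1.0 mg/dL on 2 consecutive measurements at least 3 months apart", to which the text adds a recency condition: "with the most recent one being within 4 weeks of study entry".

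The synopsis repeats exclusion 9 with the same number and the same unit. No other part of the protocol mentions PSA, gives a laboratory reporting unit for it or states a reference range. The list of changes for version 2.0 does not touch this criterion.

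Two other exclusions bear on the same patients. Exclusion 1 in section 3.2 removes "Patients receiving cancer therapy (i.e., chemotherapy, radiation therapy, immunotherapy, biologic therapy, hormonal therapy, surgery"; the synopsis version of exclusion 1 lacks that list of therapies. Exclusion 8 is a general clause on severe or uncontrolled conditions that could affect participation. Its listed examples do not include a second malignancy.

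**The concern.** The exception is built as a test of disease control. It asks for two consecutive values, separated in time, with the later one recent. That structure is useful only if the number separates controlled from uncontrolled disease. A limit in mg/dL is very large on the ng/mL scale on which PSA is ordinarily reported (laboratory convention, not stated in the documents), so on the literal text the number does not perform that task.

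Two things are at stake. First, a patient with localized prostate cancer, off cancer therapy, could satisfy the written criterion whatever the PSA. Second, if staff silently read the limit in another unit, they are applying a rule that is not in the protocol, and eligibility under this exception cannot be audited against the text.

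**Working it through.** **Inputs**
- PSA limit: below 1.0 mg/dL (section 3.2, exclusion 9; synopsis, exclusion 9).
- Conversions: 1 mg = 1,000,000 ng; 1 µg = 1,000 ng; 1 dL = 100 mL.
- The intended unit is not given in the documents, so three candidates are taken as assumptions.

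**Step 1: the printed limit in ng/mL.** 1.0 mg/dL = 1,000,000 ng / 100 mL = 10,000 ng/mL.

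**Step 2: how loose the printed limit is under each candidate unit.**

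| Unit assumed to be intended | 1.0 of that unit, in ng/mL | Printed limit ÷ intended limit |
|---|---|---|
| ng/mL | 1.0 | 10,000 / 1.0 = 10,000 |
| µg/dL | 1,000 / 100 = 10 | 10,000 / 10 = 1,000 |
| ng/dL | 1 / 100 = 0.01 | 10,000 / 0.01 = 1,000,000 |

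Under every candidate the printed limit is at least 1,000 times too loose.

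**Step 3: what the literal text lets through.** Values of 50 or 500 ng/mL are 50 / 10,000 = 0.5% and 500 / 10,000 = 5% of the printed limit, so both pass, on each of the two measurements. That the cut-off screens out essentially nobody assumes that candidates' PSA values lie below 10,000 ng/mL; the documents give no PSA distribution.

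**Step 4: what the other conditions still remove.**
- Disease that is not localized: removed by the exception itself.
- Fewer than two consecutive values, values less than 3 months apart, or no value within 4 weeks of entry: removed by the exception itself.
- Patients on cancer therapy, including hormonal therapy: removed by exclusion 1.
- Patients the investigator judges to have a severe or uncontrolled condition: may be removed under exclusion 8.
- Localized disease, off therapy, both measurements available, high PSA: the PSA cut-off is the only numeric test, and as printed it does not act.

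**Step 5: whether any statistical figure depends on the limit.** The limit is a bare threshold with no derivation to reproduce. The precision statement in section 9.1 does reproduce. With 8 CRs in 40 (20%), the exact Clopper-Pearson interval is 9.05% to 35.65%, a width of 26.60 percentage points, which agrees with "with a width of 26.6% (from 9.1% to 35.6%) for a sample size of 40 subjects". The maximum width, at 20 of 40, is 32.4 points, also as stated there. The PSA limit enters neither calculation.

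**The case against.** The strongest reply is that this is a slip that corrects itself in use. If the laboratory at this single center reports PSA in ng/mL, staff would probably compare the result with 1.0, and the literal reading would rarely operate. That is plausible and limits the practical risk. It does not settle the matter: the documents do not name the reporting unit, and an eligibility rule that works only when misread cannot be audited as written.

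A reader might infer that the criterion excludes nobody and admits patients with active prostate cancer. The documents do not support that. The numeric cut-off is idle, but the remaining conditions of the exception are not. Exclusion 1 removes patients on treatment, and exclusion 8 leaves the investigator room to refuse a patient with uncontrolled disease. The supportable statement is that such a patient could qualify, not that one would or did.

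A reader might also infer damage to the primary endpoint through prostate cancer appearing on CT or in marrow. The exception covers localized disease only, and the marrow criterion for CR in section 8.4 concerns lymphoid cells and lymphoid nodules. For PFS, section 9.6 counts death from any cause, so a death not due to CLL is an event by definition and not an analysis error. Censoring at new anticancer therapy, also in section 9.6, is a possible route, but it affects a secondary endpoint. One patient is 1/40 = 2.5 percentage points of the CR rate, but that matters only if prostate cancer changed that patient's response status, and nothing shows this. The documents give no basis for the number of patients who would use the exception.

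**Conclusion.** The point holds in a limited form. The PSA limit is printed as 1.0 mg/dL in both copies of exclusion 9. That is exactly 10,000 ng/mL, and no other text in the protocol supplies a different unit. It appears to be a unit error: a factor of 10,000 if ng/mL was intended, 1,000 if µg/dL.

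That ng/mL is the most likely intention rests on ordinary laboratory convention and on the repeated-measurement structure of the criterion, not on a statement in the documents. As written, the numeric cut-off does no screening among patients with localized prostate cancer who are off therapy; the other conditions continue to apply. Wrongful enrolment is possible but not shown, and so is any effect on CR or PFS. The sample size, the exact interval and the response definitions are unaffected. This is a minor correction to an operative eligibility rule.

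**What to change.** The investigator should confirm the intended unit (most likely ng/mL) and then correct it in exclusion 9 in both section 3.2 and the synopsis. For any patient enrolled under this exception, recheck the two recorded PSA values, with the units in which they were reported, against the confirmed limit, and document any patient who does not meet it.

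The cost is one unit in two places, carried in the next amendment, and a review of the few records concerned. No new test is needed, because the criterion already requires both PSA values. No change to the statistical section follows.

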4 STUDY DESIGN

4.1 OVERVIEW OF STUDY DESIGN

This is an open label, Phase II trial of acalabrutinib and high frequency low dose subcutaneous rituximab in previously untreated CLL patients requiring therapy. Subjects will be recruited from the James P. Wilmot Cancer Center, University of Rochester in Rochester, New York. Patients seen in the inpatient or outpatient setting with histologically confirmed untreated CLL will be evaluated for this study.

Patients will be treated with the following combination:

Rituximab: day 1 = 50 mg IV, then 50 mg SQ 2 x weekly for 6 cycles. Note that in the event of a first dose infusion reaction, subsequent doses may be given IV if felt necessary by the treating investigator.

Acalabrutinib: 100 mg po BID starting on day 8 of cycle 1. First dose prior to rituximab on day 8.

- Response assessments will be performed prior to the completion of cycle 12. Patients who have attained a radiographic complete response will undergo a BM biopsy to confirm CR. Patients in CR will also have MRD testing performed on peripheral blood and marrow. Patients in CR and undetectable for MRD, will stop therapy and be followed until disease progression.
- Patients not in a MRD negative CR, will continue acalabrutinib.
- Repeat response assessments will be performed at 24 cycles of therapy for those continuing on acalabrutinib. Patients in CR and undetectable for MRD, will stop therapy and be followed until disease progression, unacceptable toxicity or physician/patient discretion.

All cycles will be 28 days.

Patients will be followed until the occurrence of definitive disease progression and may discontinue therapy early for unacceptable toxicity or withdrawal from the study due to investigator decision or other reasons.

4.2 REGISTRATION

Patients registered to the study must sign consent after being informed of the procedures to be followed, the experimental nature of the treatment, potential benefits, alternatives, side-effects, risks and discomforts. Patients should begin study treatment within 30 days of consent.

4.3 DISCONTINUATION FROM STUDY TREATMENT

Patients will be discontinued from study treatment for any of the following reasons:

- MRD negative CR or CRI at completion of cycle 12 or cycle 24 (MRD negativity is defined as <1 CLL cell/10,000)
- Disease progression
- Severe toxicity
- Patient requests to withdraw consent or discontinue treatment
- Pregnancy

- Inability of the patient to comply with study requirements
- Conditions requiring therapeutic intervention not permitted by the protocol
- Non-compliance/lost to follow-up
- Investigator discretion
- Study termination

Patients who discontinue from study treatment (for reasons other than progressive disease) will continue to be followed for progression. After withdrawal from protocol treatment, patients should be followed for AEs for 30 calendar days after their last dose of study drug. All new AEs occurring during this period must be reported and followed until resolution, unless, in the opinion of the investigator, these values are not likely to improve because of the underlying disease. In this case the investigators must record his or her reasoning for this decision in the patient's medical records. All patients who have CTCAE Grade 3 or 4 laboratory abnormalities at the time of withdrawal should be followed until the laboratory values have returned to Grade 1 or 2, unless in the opinion of the investigator, it is not likely that these values are to improve because of the underlying disease. In this case, the investigator must record his or her reasoning for making this decision in the patient's medical records.

4.4 CRITERIA FOR STUDY TERMINATION

This study will be considered terminated when 1 or more of the following conditions are met:

- All subjects have completed all required study visits;
- All subjects have discontinued from the study;
- The University of Rochester Data Safety Monitoring Committee or Institutional Review Board (IRB) discontinues the study because of safety considerations.

